7.3 Laboratory Evaluations and Specimen Collection

7.3.1 Clinical and Research Laboratory Evaluations

Comprehensive list of clinical laboratory evaluations are detailed in the Protocol Analyte List and a comprehensive list of non-FDA approved endpoint assays are detailed in the Non-FDA Approved End Point Test List. As a reference, both lists are included in the grant application appendix, located in the study files.

7.3.2 Biohazard Containment

As the transmission of HIV and other blood-borne pathogens can occur through contact with contaminated needles, blood, and blood products, appropriate blood and secretion precautions will be employed by all personnel in the drawing of blood and shipping and handling of all specimens for this study, as currently recommended by the Centers for Disease Control and Prevention and the National Institutes of Health (NIH).

7.3.3 Specimen Preparation, Handling and Shipping

Please refer to the Specimen Management Plan included in the appendix of this grant for further details pertaining to specimen preparation, handling and shipping.

7.3.3.1 Blood

All blood samples taken in the MCRU and Positive Care Clinic will be immediately transferred to the appropriate site. Research study staff will order clinical labs (e.g. CD4 T cell count, HIV VL, CMP, and CBC) and ensure that the appropriate blood collection tubes are sent to the appropriate clinical laboratory. Samples drawn for research purposes will be transported by a scientist in the [name] lab from the MCRU to the laboratory for isolation of plasma, serum and PBMCs. Research samples obtained in the Positive Care Clinic will be transported to the [name] lab by courier and immediately processed. Please refer to the Specimen Management Plan in the study files for details regarding the distribution of serum, plasma and PBMCs to specialized laboratories for analysis.

7.3.3.2 Inguinal Lymph Node Biopsies

Lymph nodes will be harvested in the MCRU and immediately sectioned at the bedside by a study physician. For HIV infected subjects, one portion will be placed into freshly made 4% paraformaldehyde (PFA) for 24 hours (and then transferred to 80% ethanol prior to paraffin embedding) and the other is placed into RPMI and immediately transported to the [name] laboratory for preparation of cell suspension. Distribution of isolated cells is detailed in the Specimen Management Plan. For subjects enrolled in the two-photon microscopy study, a small section of the LN intended for histology will be immediately transferred fresh to the [name] laboratory. For HIV uninfected control subjects, half of the LN will be placed into fresh PFA and managed as above. The other half will be transferred fresh to the [name] laboratory.

7.3.3.3 Colonoscopy with Ileal and Rectal Biopsies

Approximately 20 snip biopsies of ileum and rectum will be obtained. Half of these samples will be placed in 4% PFA followed by 80% ethanol. They will then be paraffin embedded and used in IHC and ISH studies. The remaining samples will be immediately placed into RPMI and transferred to the [name] lab for preparation of cell suspensions. Distribution of isolated cells is detailed in the Specimen Management Plan in the study files.

8. STUDY SCHEDULE

8.1 Schedule for HIV infected subjects (n=50)

8.1.1 Screening

At this visit, consents will be reviewed in detail and the subject will have the opportunity to ask any questions they may have. Subjects will be asked if they would like to participate in the additional two-

photon microscopy sub-study which entails additional blood draws at several scheduled study visits. Designated study staff or physician will interview the participant and a physical exam (which includes vital signs and exam of heart, lungs, abdomen, neurologic and lymphatic systems) will be performed. Blood will be obtained for CD4 T cell count, HIV VL, HIV antibody, liver function tests, electrolyte panel including creatinine, and complete hematology count (CBC - white blood cell count with differential, hemoglobin and platelets). Screening for hepatitis C will also be performed. Women of childbearing age will have a urine pregnancy test. Once lab results are available (within 3 days), they will be reviewed by designated study staff to ensure that laboratory inclusion/exclusion criteria are met. If the subject has met all entry criteria, they will be contacted by the designated study staff. The study protocol will again be reviewed and if they are still interested in enrolling, they will be scheduled for the day 0 visit. Subjects who have not met the criteria will also be contacted by the designated study staff and told that they do not qualify to participate in the study. At this visit, an "enroll by date" will be designated that is no more than 60 days from the screen date to ensure screening labs are no more than 60 days old at the time of randomization. If more than 60 days passes between "Screen" and randomization, a comprehensive chemistry panel will be redrawn with the results known to be within study-required parameters prior to randomization.

8.1.2 Baseline Visit

Designated study staff will review medical history with the participant and perform a targeted physical exam (vitals, heart, lung, abdomen, neurologic system). The subject will not be randomized until lab results have been reviewed and found to be within limits designated in the protocol. The designated study staff or principal investigator will sign off on lab results and eligibility criteria on the day of randomization to ensure labs are no more than 60 days old and the subject still meets all eligibility criteria. Blood will then be drawn for CBC, comprehensive metabolic panel (CMP – includes electrolytes, creatinine, and liver function tests), CD4 and VL as well as plasma, serum and PBMCs for study endpoints. Subjects in the two-photon microscopy sub-study will also have an additional 90cc of blood drawn. Inguinal LN biopsy and colonoscopy with ileal and rectal biopsies will be performed (described in detail in section 7.1 above). They will remain in the MCRU for 4 hours after procedures for monitoring.

Following procedures, subjects will be randomized to receive either losartan or placebo. The drug will be dispensed to the participant to begin administration on that day. At this baseline visit, participants will start losartan or matching placebo at 50mg daily. Prior to the first dose, the subject will be counseled regarding dosing schedule, potential side effects, and the importance of adherence. A member of the study team will contact the subject by telephone at day 7 to check for tolerability.

8.1.3 Day 14 Visit

Subjects will be seen at day 14 for clinical assessment (interval history and targeted exam), assessment of drug adherence and to obtain toxicity labs (CBC and CMP). If the subject meets the following criteria: lack of dizziness, lightheadedness, or faintness upon rising, confusion, palpitations, and cough; GFR greater than or equal to 30 mL/min/1.73 m² and potassium level less than or equal to 5.0, the dose of losartan/placebo will be increased to 100 mg po daily. The maximal tolerable dosage (up to 100 mg a day) will be continued for a total of 30 months.

At Day 14, side effects and blood chemistries (comprehensive chemistry panel) will be assessed. The dose of losartan/placebo will increase to 100mg daily at this Day 14 visit (i.e., once lab results return) if all of the following criteria are met:

- a) Systolic blood pressure (BP) ≥ 90 mmHg
- b) Potassium ≤ 5.0 mmol/L
- c) eGFR ≥ 30 mL/min/1.73m²

- d) Lack of a grade ≥ 3 side effect since the last evaluation deemed possibly/probably related to the study drug.
- e) Lack of significant side effects deemed related to study drug (e.g., lightheaded upon standing)
- f) Lack of other concerns to increase study drug dosing, as determined by site investigator

Participants may be evaluated by clinical labs and/or have side effects assessed at any point during the study, per the discretion of the site investigator. If participants are increased to 100mg daily (or matching placebo) they will maintain this dose for the duration of the 30-month study unless new side effects or adverse events necessitate re-evaluation (see below criteria for dose reduction or stopping study medication).

If participants do not increase dose to 100mg daily at the week 2 visit (e.g., if symptomatic or if systolic BP is not ≥ 90 mmHg), the criteria for dose escalation may be reassessed at the 1-month visit. If participants do not meet criteria for dose increase (from 50mg to 100mg daily) after the 1-month visit, they will be maintained on 50mg dose until the month 3 visit, at which time the dose may be increased to 100mg daily if the first five criteria above are met (a-e). At any point when participants have dose increased from 50mg to 100mg, they will be contacted by phone within 2 weeks to assess side effects and have clinical labs drawn to assess toxicity; a full study visit for side effect and adverse event documentation can occur at any point, per the discretion of the site investigator.

Dose Reduction: Tolerability, side effects, and clinical laboratory monitoring will be assessed at each study visit (via participant report and clinical labs), and at any other time point at the discretion of the clinical site investigator. Adverse events that are assessed as related to study drug will prompt re-evaluation via phone or as an adverse event visit, per clinical discretion of the site investigator. If this event worsens or does not resolve after re-evaluation, then study medication dose should be decreased (i.e., from 100mg to 50mg) or stopped (if taking 50mg daily). If signs and symptoms resolve after 2 weeks, then the participant may resume or increase dose (i.e., back to 100mg if previously reduced to 50mg daily), per the clinical discretion of the site investigator.

Stopping Study Medication: If an adverse event of grade ≥ 3 is assessed as related to study drug, study medication should be stopped and the participant should be re-evaluated in 2 weeks. If a grade 2 rash is persistent, study medication may also be stopped at the discretion of the site investigator and the participant should be re-evaluated in 2 weeks. If signs and symptoms resolve after 2 weeks, then the participant may be re-challenged at a lower dose (i.e., at 50mg if previously taking 100mg daily) per the clinical discretion of the site investigator. If study medication is stopped for an adverse event that is later determined NOT to be related to study medication, then the medication may be resumed at 50mg and increased to 100mg per initial criteria for dose escalation and at the discretion of the clinical site investigator.

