2.2 Study Hypothesis and Rationale

Our hypothesis is that treatment of HIV infected subjects with losartan, which has specific anti-inflammatory and anti-fibrotic actions will: 1) reverse existing fibrosis, 2) restore LN architecture, 3) increase the number and improve the function of peripheral and lymphatic CD4 T cells, 4) decrease levels of IA, 5) decrease HIV reservoirs, and 5) be safe and well tolerated. To address this hypothesis, we will enroll HIV infected subjects and randomize them 1:1 to losartan vs placebo, then serially sample blood and LT. In similar longitudinal tissue biopsy protocols our drop-out rate has ranged from 20-25%. Therefore, we plan to enroll 63 HIV infected subjects in order to have 50 complete the protocol. All HIV infected subjects randomized to losartan will initiate therapy at a dose of 50 mg per os (po) daily and increase the dose to 100 mg po daily if they have no side effects or laboratory abnormalities after 14 days. This is standard losartan dosing for the treatment of hypertension and stroke reduction. This dosing protocol was also used and was well tolerated by non-hypertensive subjects in a large clinical trial assessing the anti-fibrotic effect of losartan in patients with Marfan syndrome [48]. Given risk of teratogenicity with losartan, all female subjects of reproductive age who are enrolled in the protocol will be required to use a reliable and effective method of contraception for the duration of the study. Lymphatic tissue biopsies for primary endpoint analysis will be obtained at baseline and 12 and 30 months after initiation of losartan or placebo. We are following subjects for 30 months because we felt that a long period of follow up may be required to discern a significant difference in the treatment groups given the persistence of LT fibrosis in subjects treated with ART alone (unpublished data). HIV infected subjects will also be administered the human papillomavirus (HPV) quadrivalent vaccine (Gardasil) per the manufacturer's recommended dosing schedule to assess immune response (a secondary endpoint). Gardasil vaccine is FDA-approved for use in men and women ages 9 to 26 to prevent the complications related to infection with HPV types 6, 11, 16 and 18. Although not approved for adults >26 years of age, the vaccine has been well-studied in older populations and has been found to be safe and well-tolerated [49-51]. It is expected that many study subjects will have been exposed to 1 or more of the HPV serotypes included in the vaccine; however, based on epidemiologic data, it is not expected that subjects will have been exposed to all 4 serotypes [52-54]. Therefore, this vaccine can be used to assess both neo and recall immune responses. Vaccination will be initiated at the end of the study to maximize time on study drug prior to vaccination and to ensure that tissues are collected at time of maximal immune response.

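### Section 8.1.3 states the day-14 dose step twice, with criteria that conflict in both directions, and nothing says which statement governs.

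*Combined protocol and SAP*

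**What the plan says.** Section 8.1.3 (Day 14 Visit) opens with one rule. The conditions are "lack of dizziness, lightheadedness, or faintness upon rising, confusion, palpitations, and cough" together with "GFR greater than or equal to 30 mL/min/1.73 m² and potassium level less than or equal to 5.0". If they are met, "the dose of losartan/placebo will be increased to 100 mg po daily". The symptoms carry no qualifier of cause or severity, and the paragraph does not mention blood pressure.

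The next paragraph states the step again. The dose "will increase to 100mg daily at this Day 14 visit (i.e., once lab results return) if all of the following criteria are met". The six lettered items are:

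- a: "Systolic blood pressure (BP) ≥ 90 mmHg".
- b and c: the same potassium and eGFR limits as in the first paragraph.
- d: no grade 3 or higher "side effect since the last evaluation deemed possibly/probably related to the study drug".
- e: no significant side effect attributed to study drug, with lightheadedness on standing as the example.
- f: no other concern of the site investigator.

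Two other places describe the step in a single sentence each. Section 2.2 says that participants on losartan will "increase the dose to 100 mg po daily if they have no side effects or laboratory abnormalities after 14 days". Section 6.1.1.2 says the week-2 increase rests on tolerability, blood pressure and toxicity laboratory results, and gives no thresholds.

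The rest of section 8.1.3 refers back to these rules. The escalation criteria may be reassessed at month 1. The month-3 step cites items a to e. Resumption after an event found to be unrelated to study drug uses the initial escalation criteria.

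**The concern.** Each statement is worded as enough on its own to trigger the increase, and neither contains the other. Whether a given participant goes up or stays can therefore depend on which paragraph staff apply.

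The issue is one of safety. Hypertension is not an entry criterion, and section 2.4.1 names symptomatic hypotension among the most severe risks of losartan. Yet the first rule a reader meets at the dose step is silent on blood pressure. The ambiguity also carries forward, because the month-1 and resumption references name escalation criteria without saying which statement they mean.

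**Working it through.** No sample size, power or error rate is involved, so there is no plan figure to reproduce. The check sets the two statements in section 8.1.3 side by side and applies both to the same hypothetical participants.

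**Item by item**

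| Item | First paragraph | Lettered list |
|---|---|---|
| Systolic pressure | absent | at least 90 mmHg (a) |
| Potassium | at most 5.0 | at most 5.0 (b) |
| GFR | at least 30 | at least 30 (c) |
| Graded toxicity | absent | no grade 3 or higher, possibly or probably related (d) |
| Symptoms | six named, any cause, any severity | only if significant and drug-related (e) |
| Investigator concern | absent | none (f) |

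The two laboratory limits agree. The other four rows differ.

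**Hypothetical participants, otherwise normal**

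| Case | First paragraph | Lettered list |
|---|---|---|
| 1. No findings | increase | increase |
| 2. Potassium 5.4 | hold | hold |
| 3. Systolic 85, no symptoms | increase | hold (a) |
| 4. Investigator concern only | increase | hold (f) |
| 5. Cough judged unrelated | hold | increase, unless f is invoked |
| 6. Mild related dizziness judged not significant | hold | increase, unless f is invoked |

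Cases 3 and 4 conflict in one direction, cases 5 and 6 in the other.

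**How firm each case is**

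- Case 3 needs no interpretation. All the conditions of the first paragraph are satisfied, and later text in the same section gives systolic pressure not reaching 90 as a reason for no increase.
- Case 5 takes a participant who fails the first paragraph to be held, which is the ordinary reading of a conditional instruction. Under the list, an unrelated cough does not breach items d or e, so only item f could stop the increase.
- Case 6 depends on what counts as significant in item e, and is weaker.
- A related grade 3 event would also split the two statements on paper. It is not used here, because the stopping text in section 8.1.3 would apply to it in any case.

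**Carry-forward**

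Of the later references, only the month-3 step identifies its criteria by letter. It also leaves out item f. A participant held at day 14 for an unrelated cough under the first paragraph could therefore satisfy a to e at month 3 with the same cough.

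**The case against.** The best case against is that the lettered list plainly governs. The blood pressure example and the month-3 citation of a to e refer only to that list, and section 6.1.1.2 names blood pressure. Someone who reads the whole section meets low pressure as a bar more than once. Item f also lets the investigator hold a participant with cough, palpitations or confusion, so the reverse conflict is an automatic bar against a judgement. These signals are strong, but they are not a precedence rule. The first paragraph still stands as an instruction at the head of the section.

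Reading the two cumulatively does not rescue the text. The first paragraph is written as sufficient for the increase, not as an added condition. Its bar on any lightheadedness would also leave the narrower example in item e with nothing to do.

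The safeguards are real and limit the consequence:

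- Section 5.2 excludes a screening systolic pressure below 110.
- Section 8.1.2 schedules a tolerability call at day 7.
- Section 8.1.3 requires telephone contact and toxicity laboratory tests within 2 weeks of any increase.
- Section 8.1.3 also contains dose-reduction and stopping rules.

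A reader might infer that section 2.2 adds a third operative list. Taken literally, it would hold someone whom both statements in 8.1.3 would escalate, for example a participant with an eGFR of 45 if that counts as a laboratory abnormality. But it is one sentence of rationale with no thresholds, grades or attribution. It should be aligned, but it is not a competing visit instruction.

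**Conclusion.** Wrong as written. Section 8.1.3 contains two day-14 rules that give opposite decisions for the same participant, in both directions, and no text resolves them. The clearest case is a symptom-free participant with systolic pressure below 90.

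The size is unknown. The plan is for 50 HIV-infected participants to complete, with 63 enrolled. Those numbers bound who can reach the decision; they do not count who is affected. The documents give no frequencies of low pressure, cough or mild dizziness at day 14, so the discordant share cannot be derived. A participant with no findings is escalated under both statements.

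Two stronger readings are not supported. The first is that the conflict changes the dose the trial tests. Dosing is to tolerance by design, and a participant held at day 14 can be reassessed at months 1 and 3 of a 30-month study, so a lasting dose difference is not shown. The second is that the conflict biases the comparison between arms. The trial is single-centre, and the staff who make the decision are blinded, so nothing in the documents points to a differential effect.

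The conclusion rests on the wording alone. It takes no view on which criteria are clinically right.

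**What to change.** The sponsor should:

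1. Reconcile the two paragraphs of section 8.1.3 into one governing list and delete the other statement.
2. Make the month-1, month-3 and resumption references point to that list by name, and state whether the omission of item f at month 3 is intended.
3. Align the summary sentences in sections 2.2 and 6.1.1.2, or replace them with a cross-reference.

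Which criteria the single list contains is for the sponsor to decide, and none is proposed here. The cost is protocol wording only. No visit, sample, assay or analysis changes because of the clarification itself.

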2.4 Potential Risks and Benefits

2.4.1 Potential Risks

Potential risks of study procedures (venipuncture, inguinal LN biopsy, and colonoscopy with GALT biopsies) are detailed in Section 7.1 and in consent forms. According to the Losartan package insert, the most severe risks of losartan use include teratogenicity in the setting of pregnancy, hypersensitivity, symptomatic hypotension, worsening of renal function, and electrolyte abnormalities. The most common side effects of losartan include fatigue, weakness, diarrhea, chest pain, tachycardia and anemia.

Subjects will be rigorously screened to ensure that they are at low risk for complications due to losartan and they will be monitored closely for side effects and signs of toxicity. The most common side effects of Gardasil include headache, fever, nausea, dizziness and injection site reactions. Severe reactions, including hypersensitivity, are rare. The most common side effects of Stribild are new onset or worsening of renal impairment, bone effects, fat distribution and immune reconstitution syndrome. The most common side effects of Stribild include nausea, diarrhea, abnormal dreams, headache, rash, fatigue, dizziness, insomnia, flatulence, somnolence, ocular icterus and jaundice. The most common side effects of Prezista are drug –induced hepatitis, skin reactions ranging from mild to severe, use with caution with a known sulfonamide allergy, new onset diabetes or hyperglycemia, redistribution/accumulation of body fat or immune reconstitution syndrome and subjects with hemophilia may develop increased bleeding events, The most common side effects of Prezista include diarrhea, nausea, rash, headache, abdominal pain and vomiting.

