7.2 Plan to Minimize Risks to Subjects

All investigators and study staff have completed required training regarding human subject protections. Study staff will comply with all related regulations and laws, included, but not limited to 45 CFR 46 and 21 CFR 50, 56 (FDA version), and HIPAA Privacy Regulations. Study will be conducted in accordance with US and international standards for good clinical practices, applicable regulations, and institutional research policies and procedures.

Subjects will be rigorously screened against inclusion/exclusion criteria to ensure that their participation is safe. All staff members responsible for taking a medical history that could potentially make the participant uncomfortable have been specifically trained for how to do this in a sensitive manner. Only qualified study or clinic staff or physicians will draw blood to minimize risks. Pregnancy testing will be performed at screening, baseline, every 3 months, and anytime during follow up when the woman or investigator suspects pregnancy. In addition, study staff will stress the importance of adherence to contraceptives in order to minimize risks related to unintended fetal exposure. Subjects will be closely observed for systemic adverse events and toxicity related to the study drug on a routine basis through interviews, clinical assessment (including measuring vital signs and physical exam), and monitoring of renal function, liver function, and hematologic panel. All lymph node biopsies will be performed by either [name], [name], or [name] who have performed >400 LN biopsies in the research setting without significant complications. All colonoscopies will be performed by [name] who has performed >300 colonoscopies and biopsies in related HIV studies in the past without any complications. Subjects will be monitored after biopsy procedures for at least 4 hours by study staff trained in managing postoperative patients. They will be monitored for at least 30 minutes after HPV vaccine administration to ensure that they tolerate the vaccine without difficulty.

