8.1.5 Months 3, 6, 9, 15, 18, 21 and 27 Visits

Subjects will be seen for clinical assessment (interval history and targeted exam), review of drug adherence, refill of study drug, and blood draw for CBC, CMP, CD4, VL, plasma, serum and PBMCs.

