8.1.8 Month 25 visit

Subjects will return for clinical assessment (interval history and targeted exam), review of drug adherence, refill of study drug and blood draw for plasma, serum and PBMCs. The second dose of Gardasil will then be administered. Subjects will remain in the MCRU for 30 minutes after administration for monitoring.

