8.2 Schedule of Events for HIV Infected Subjects

Table 1. Protocol summary for HIV infected subjects:

	Screen	Day 0	Day 14	Month 1	Months 3, 6, 9, 15, 18, 21, 27	Month 12	Month 23	Month 25	Month 29.5	Month 30
Medical history	X	X								
Interval medical history			X	X	X	X	X	X	X	X
Physical Exam ¹	X	X	X	X	X	X	X	X	X	X
Adherence assessment and counseling		X	X	X	X	X	X	X	X	X
Pregnancy test ²	X	X		X	X	X		X	X	
HCV Ab	X									
CMP	X	X	X	X	X	X	X		X	X
CBC w diff	X	X	X	X	X	X	X		X	X
CD4 count	X	X		X	X	X	X		X	X
HIV viral load	X	X		X	X	X	X		X	X
Serum ³		X		X	X	X	X	X	X	X
Plasma /PBMCs ⁴		X		X	X	X	X	X	X	X
Additional PBMCs ⁵		X				X				X
Biopsies ⁶		X				X				X
HPV vaccine ⁷							X	X	X	
PK assessment				X ⁸	X ⁹	X ⁹		X ⁹		X ¹⁰

1. At screening, a full physical exam will be performed (described above). At subsequent visits, a targeted exam will be performed.
2. Women of childbearing age must have a negative pregnancy test prior to enrollment. Pregnancy testing will also occur roughly every 3 months during follow up and additionally if the subject or investigator suspects pregnancy.
3. Serum will be used to determine levels of IL-7 and TGF-beta.
4. Plasma will be used to determine levels of cytokines and markers of inflammation. PBMCs will be used in flow cytometry and intracellular cytokine staining.
5. Additional blood will be obtained from subjects enrolled in the two-photon microscopy sub-study.
6. Inguinal LN biopsy and colonoscopy with sampling of ileal and rectal tissues.
7. Human papillomavirus quadrivalent vaccine (Gardasil) will be administered at 3 time points per recommended vaccine schedule and immune response will be assessed at month 30.
8. Intensive 24-hour PK assessment will be performed at month 1 visit.
9. Plasma and intracellular PBMC concentration of losartan and ARVs will be determined approximately every quarter.
10. Plasma and intracellular PBMC concentration of losartan and ARVs PLUS concentrations in LN and GALT will be determined at month 30.

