9.3 Recording and Documentation of AEs

At each contact with the subject, designated study staff must seek information as to discomforts or adverse experiences by specific questioning and, as appropriate, by examination. At study visits, safety laboratory evaluations will also be performed to identify any laboratory AEs. All side effects will be reported to the PI and/or physician co-investigators on a daily basis and toxicity laboratory results will be reviewed in real time. Information about AEs to be recorded includes event description, time of onset, investigator assessment of severity, relationship to study agent(s)/Intervention(s), and time of resolution/stabilization of the event. All AEs occurring during the study period (from time of consent signing to 3 months after the last study visit) must be documented appropriately regardless of relationship to study products or procedures. Information on all AEs will be promptly recorded in the source document and also in the appropriate AE module of the case report form (CRF).

Any medical condition that is present at the time that the participant is screened should be considered as baseline and not recorded as an AE. However, if the condition deteriorates at any time during the study it should be recorded and reported as an AE. Changes in the severity of an AE should be documented to allow an assessment of the duration of the event at each level of intensity to be performed. Adverse events characterized as intermittent require documentation of the onset and duration of each episode. Changes in the assessment of relationship to the study agent(s)/interventions should also be clearly documented.

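### Section 8.1.3 puts clinical labs at each study visit, but no CMP or CBC is scheduled at month 25, which leaves one 4-month interval between safety panels

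*Combined protocol and SAP*

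**What the plan says.** The dose-reduction paragraph of section 8.1.3 gives the general rule: "Tolerability, side effects, and clinical laboratory monitoring will be assessed at each study visit (via participant report and clinical labs". It then allows further assessment at other times at the site investigator's discretion, so discretionary labs come on top of the visit labs. Section 9.3 is similar but looser: "At study visits, safety laboratory evaluations will also be performed to identify any laboratory AEs".

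At the ordinary quarterly visits, section 8.1.5 lists "refill of study drug, and blood draw for CBC, CMP, CD4, VL, plasma, serum and PBMCs". Sections 8.1.6 and 8.1.7 list the same tests at months 12 and 23. For month 25, section 8.1.8 lists only "refill of study drug and blood draw for plasma, serum and PBMCs". The schedule in section 8.2 ("Table 1. Protocol summary for HIV infected subjects") agrees with 8.1.8: the CMP and CBC rows are blank in the month 25 column and marked in every other column.

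**The concern.** A site cannot follow both texts at month 25. If it works from Table 1, it departs from 8.1.3. If it works from 8.1.3, it draws panels that Table 1 does not ask for.

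The panels matter because section 2.4.1 says that "the most severe risks of losartan use include teratogenicity in the setting of pregnancy, hypersensitivity, symptomatic hypotension, worsening of renal function, and electrolyte abnormalities". Section 7.2 offers, as one of the protections, "and monitoring of renal function, liver function, and hematologic panel". Section 8.1.2 describes the CMP as the test that covers electrolytes, creatinine and liver function. The dose-reduction, stopping and withdrawal rules (8.1.3, 9.6, 9.7.2) work only if toxicity is detected, and the history and examination at month 25 cannot be relied on to show a potassium or creatinine change without symptoms. Participants are still on study drug and receive a further supply at that visit. What is at stake is how promptly a silent laboratory toxicity is found late in the study. The efficacy analysis is not involved.

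**Working it through.** The plan gives no figure of its own to reproduce, so the check is a count of visits and intervals.

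**Visits.** Table 1 has 14 visits after day 0: day 14; month 1; months 3, 6, 9, 15, 18, 21 and 27; and months 12, 23, 25, 29.5 and 30. CMP and CBC are marked at 13 of them. The text for month 1 (8.1.4) says only that blood is drawn, but Table 1 marks both panels there, so it is not a second gap. Ten visits include a refill in sections 8.1.5 to 8.1.8 (months 3, 6, 9, 12, 15, 18, 21, 23, 25 and 27). Month 25 is the only one of these without the panels.

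**Intervals.** Taking day 14 as 0.5 month, the scheduled panels fall at 0, 0.5, 1, 3, 6, 9, 12, 15, 18, 21, 23, 27, 29.5 and 30 months. The gaps are 0.5, 0.5, 2, 3 (six times), 2, 4, 2.5 and 0.5, which sum to 30. The longest is 4 months (23 to 27) and the next longest is 3.

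**How Table 1 treats the months around 24:**

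| Item | Month 21 | Month 23 | Month 25 | Month 27 |
|---|---|---|---|---|
| CMP, CBC | yes | yes | no | yes |
| CD4, viral load | yes | yes | no | yes |
| Pregnancy test | yes | no | yes | yes |
| Drug levels | yes | no | yes | yes |

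There is no month 24 visit. Each quarterly item appears once between months 21 and 27, either at 23 or at 25.

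**Size.** If an abnormality starts at a uniformly random time, the mean wait to the next scheduled panel is the sum of squared gaps divided by twice the length of the period. Over months 21 to 27:

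- As planned (21, 23, 27): (2² + 4²)/(2 × 6) = 20/12 = 1.67 months.
- Even quarterly schedule (21, 24, 27): (3² + 3²)/12 = 18/12 = 1.50 months.
- Excess: 0.17 month, about 5 days at 30.44 days per month.
- With a month 25 panel added (21, 23, 25, 27): (2² + 2² + 2²)/12 = 1.00 month.

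Over all 30 months the sum of squared gaps is 85 as planned and 77 with a month 25 panel. The mean wait goes from 85/60 = 1.42 to 77/60 = 1.28 months, a gain of 8/60 = 0.13 month, about 4 days. The longest interval goes from 4 to 3 months.

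**People.** The losartan-specific risk applies to about 50/2 = 25 of those expected to complete, and to at most 63/2, about 32.

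**The case against.** The best case for the plan is that the blank is deliberate. Table 1 and 8.1.8 agree with each other, and the pregnancy and drug-level rows are the mirror image of the CMP and CBC rows. That looks like one quarterly visit shared between two vaccine visits. The same split puts 4 months (21 to 25) between pregnancy tests and between drug-level samples, and the footnotes to Table 1 describe both as only approximately quarterly. The documents set no maximum interval between panels. All of this stands. A reader might infer that the panels were forgotten, or that a stated limit is breached; the documents support neither.

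A reader might also infer that section 9.3 independently requires labs at every visit. It does not say each or every, and panels are drawn at 13 of 14 visits, so the conflict rests on 8.1.3.

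A reader looking at months 23 to 27 alone would compare a mean wait of 4/2 = 2.0 months with 3/2 = 1.5 and report an excess of 0.5 month, about 15 days. That ignores the shorter 2-month gap just before it. The 4-month gap arises because the month 24 panel was in effect drawn a month early, and the fair comparison gives about 5 days.

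Nor is month 25 unmonitored. It has an interval history, a targeted examination with vital signs, an adherence review, a pregnancy test and drug levels. Under 8.1.3, "Participants may be evaluated by clinical labs and/or have side effects assessed at any point during the study", at the investigator's discretion. These safeguards are real, but they need a prompt: drug levels lead to toxicity labs only if a level is out of range or an interaction appears (7.2), and discretionary labs depend on someone suspecting a problem.

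**Conclusion.** The inconsistency is real. Section 8.1.3 calls for clinical labs at each visit, and the schedule omits them at month 25 alone. The result is one 4-month interval between safety panels, against at most 3 months elsewhere for CMP and CBC. The split around month 24 may be intended; intent would decide which text to correct but would not remove the conflict.

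The consequence is small: about 5 days of extra mean wait over months 21 to 27 compared with even quarterly panels, and no effect on any endpoint. The figure assumes uniform onset, visits on their nominal dates and no unscheduled labs, so it describes the schedule and does not predict any actual delay. This is a low-cost improvement to consider, not a safety failure.

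**What to change.** Mark CMP and CBC in the month 25 column of Table 1 and add both to the blood draw in 8.1.8. The schedule then matches 8.1.3, and the longest scheduled interval falls from 4 to 3 months. The cost is a short amendment and one extra CMP and CBC for each participant who reaches month 25 (about 50, at most 63). Blood is already drawn at that visit, so no extra needle is needed.

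If the sponsor confirms that the lighter month 25 visit is intended, limiting 8.1.3 to the visits marked in Table 1, and aligning 9.3 with it, would remove the conflict without added tests. That is only a clerical correction, and it leaves the 4-month interval in place. Adding the panels is the better choice.
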